11.6.3. Safety

Time to Death endpoint

- Time to Death is defined as follows:
For subjects who died, time to death is the date of death - start date +1.
For subjects who did not die, time to death (censored) is the censoring date – start date + 1.
Occurrence and date of death will be determined based on data recorded in the CEC Death form; if adjudicated death date is missing then investigator-reported death date will be used.
Start date and censoring date will be assigned based on the evaluation time period of interest as subsequently specified.

Evaluation Time Period for Vital Status

Time Period for Follow-up of Vital Status

The start date of the time period for capturing vital status is the date of randomization. The end of this time period is defined as follows:

- For all subjects known to have died, use the date of death
- Otherwise, use the Last Study Contact Date.

Any endpoints that occurred before the start of this time period are considered to be prior to the time

Time to Death endpoint
period for vital status, and any endpoints that occurred after the end of this time period are considered to be post the time period for vital status.
Time Period for On-treatment Deaths
The start date of the time period for capturing On-treatment deaths is the treatment start date for subjects who received study treatment, and the date of randomization otherwise. The end of this time period is defined as follows: 
 For subjects who did not receive study treatment, use the date of randomization For all subjects known to have died, use the earliest of the following two dates: treatment stop date and date of death. Otherwise, use the earliest of the following two dates: treatment stop date and Last Study Contact Date. If the censoring date as defined above for On-treatment deaths is after the censoring date as defined for the time period for follow-up of vital status, then use the censoring date as defined for the time period for follow-up of vital status. Any events that occurred before the start of this time period are considered to be prior to the time period for On-treatment deaths, and any events that occurred after the end of this time period are considered to be post the time period for On-treatment deaths.
Time Period for On-therapy Deaths
The start date of the time period for capturing On-therapy deaths is the treatment start date for subjects who received study treatment, and the date of randomization otherwise. The end of this time period is defined as follows: 
 For subjects who did not receive study treatment, use the date of randomization. For all subjects known to have died, use the earliest of the following two dates: treatment stop date + 56 days and date of death. Otherwise, use the earliest of the following two dates: treatment stop date + 56 days and Last Study Contact Date. If the censoring date as defined above for On-therapy deaths is after the censoring date as defined for the time period for follow-up of vital status, then use the censoring date as defined for the time period for follow-up of vital status. Any events that occurred before the start of this time period are considered to be prior to the time period for On-therapy deaths, and any events that occurred after the end of this time period are considered to be post the time period for On-therapy deaths.

 Endpoint person-years = (cumulative total time to death for subjects who died + cumulative total of censored time for subjects without the event) / 365.25 Incidence rate (per 100 person-years) = (100 * number of subjects who died) / endpoint person-years Endpoint absolute rate difference (per 100 person-years) = albiglutide incidence rate (per 100

Time to Death endpoint

person-years) – placebo incidence rate (per 100 person-years)

Adverse Events

General definitions

- Time to first AE is defined as follows:
For subjects who had at least one AE of interest, time to first AE = onset date of first AE – treatment start date + 1.
For subjects who did not have at least one AE of interest, time to first AE (censored) is the censoring date – treatment start date + 1.
Censoring date will be assigned based on the evaluation time period of interest as subsequently specified.
- AE incidence rate (per 100 person-years) = $(100 * \text{number of subjects with at least one AE}) / \text{first AE person-years}$
- First AE person-years = $(\text{Cumulative total of time to first AE for subjects who have the AE} + \text{Cumulative total of censoring time for subjects without the AE}) / 365.25$
- AE density, also referred to as event density, will be calculated for specified AEs. AE density = number of events / AE density person-years and will be presented per 100 person-years.
- AE density person-years = cumulative total of censoring time / 365.25, where censoring time is the censoring date – treatment start date + 1. Censoring date will be assigned based on the evaluation time period of interest as subsequently specified.

Time Period for On-treatment AEs

The time period for capturing On-treatment AEs begins at treatment start date. The end of this time period is the earliest of the following two dates: treatment stop date, latest of clinic visits, phone calls and other contact with subject.

Any events that occurred before the start of this time period are considered to be prior to the time period for On-treatment AEs, and any events that occurred after the end of this time period are considered to be post the time period for On-treatment AEs.

Time Period for On-therapy AEs

The time period for capturing On-therapy AEs begins at treatment start date. The end of this time period is the earliest of the following two dates: treatment stop date + 56 days and latest of clinic visits, phone calls and other contact with subject.

Any events that occurred before the start of this time period are considered to be prior to the time period for On-therapy AEs, and any events that occurred after the end of this time period are considered to be post the time period for On-therapy AEs.

Time Period for On-therapy and Post-therapy AEs
--

The time period for capturing On-therapy and Post-therapy AEs begins at treatment start date. The

end of this time period is the latest of the following: latest of clinic visits, phone calls and other contact with subject, latest non-missing AE start date, latest non-missing AE end date.

Any events that occurred before the start of this time period are considered to be prior to the time period for On-therapy and Post-therapy AEs, and any events that occurred after the end of this time period are considered to be post the time period for On-therapy and Post-therapy AEs.

AEs of Special Interest

Following are the protocol-specified AEs of special interest:

- Development of thyroid cancer
- Haematologic malignancy
- Pancreatic cancer
- Pancreatitis
- Investigational Product Injection site reactions
- Immunological reactions
- Severe hypoglycaemic events
- Hepatic events
- Hepatic enzyme elevations (including GGT)
- Serious GI events
- Appendicitis
- Atrial fibrillation/flutter
- Pneumonia
- Worsening renal function
- Diabetic retinopathy

For some of these AESIs (development of thyroid cancer, pancreatitis, investigational product injection site reactions, immunological reactions, severe hypoglycaemic events, atrial fibrillation/flutter, pneumonia, worsening renal function, diabetic retinopathy), event-specific details are recorded in the eCRF. Generally, the presence of these details will be used to identify these AESIs. However, for diabetic retinopathy, events will be identified if a diagnosis of diabetic retinopathy (background, pre-proliferative, or proliferative) for at least one eye is recorded on the Diabetic Eye Disease Event eCRF.

For the remaining AESIs (haematologic malignancy, pancreatic cancer, hepatic events, hepatic enzyme elevations (including GGT), serious GI events, appendicitis), these will be determined based on sets of coded terms as defined by safety review team (SRT) agreements. Per the protocol Section 6.2.3, severe hypoglycaemic events are defined as those episodes of hypoglycaemic symptoms for which the subject required assistance from another person and from which the subject recovered promptly after resuscitative actions and also including episodes of hypoglycaemic symptoms which are SAEs.

Pancreatitis events will be considered to be positively adjudicated if "Probability of Pancreatitis" = "Definite" or "Probability of Pancreatitis" = "Possible" as determined by the PAC.

Malignant Neoplasms

Malignant neoplasms are defined by SRT agreements.

Other CV Events

Following are the protocol-specified other CV events:

- Arrhythmias
- Valvulopathy

- Pulmonary hypertension
- Peripheral Arterial Thromboembolism
- Deep Venous Thrombosis/Pulmonary Embolism
- Revascularization (other than revascularizations intended for CEC adjudication)

Arrhythmias will be determined based on data recorded in the Arrhythmia eCRF form excluding events that are indicated as having electrocardiogram (ECG) result of only "Atrial flutter" and/or "Atrial Fibrillation". Revascularization (other than revascularizations intended for CEC adjudication) will be determined based on data recorded in the percutaneous coronary intervention (PCI) eCRF form and the coronary artery bypass graft (CABG) eCRF form excluding events indicated as reason = "Acute coronary syndrome".

The remaining other CV events will be determined based on presence of data recorded in event-specific forms in the eCRF.

EGFR

eGFR will be computed based on measured creatinine and associated age using the formula specified in Section 6.2.6.1 in the protocol and reported in units of ml/min/1.73m². For this purpose associated age, in whole years, will be calculated with respect to the date of creatinine sample using the imputed date of birth (see Section 11.6.2).

nonHDLc

nonHDLc = TC - HDLc

If there are multiple values per date, compute nonHDLc as the maximum TC – maximum HDLc; if this results in a value < 0 then set to missing.

Albuminuria

History of albuminuria will be determined based on data recorded in the Nephropathy history eCRF (none, microalbuminuria, macroalbuminuria). Post-baseline albuminuria will be determined based on data recorded in the Renal Impairment eCRF (none, microalbuminuria, macroalbuminuria).

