11.4.2. Treatment States for AE data

Treatment State	Definition
Pre-therapy	AE Start Date < Study Treatment Start Date
On-therapy (during treatment or up to 56 days post-treatment)	If AE onset date is on or after treatment start date & within 56 days after treatment stop date. Study Treatment Start Date ≤ AE Start Date ≤ Study Treatment Stop Date+56 days
Post-therapy	If AE onset date is after the treatment stop date+56 days. AE Start Date > Study Treatment Stop Date+56 days

NOTES:

- If the study treatment stop date is missing then the AE will be considered to be On-therapy.

If only partial information is available for the onset date of an AE, or onset date is missing, then the AE will be included in the most conservative therapy period (On-therapy > Post-therapy > Pre-therapy) that is consistent with the therapy period definitions above and the available AE onset and resolution date information.

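### Sections 11.4.2 and 11.6.3 define On-therapy adverse events differently, and the 11.6.3 rule can leave fatal SAEs that start after the last subject contact out of the On-therapy displays

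*SAP*

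**What the plan says.** Section 11.4.2 (treatment states for AE data) sets the On-therapy state by onset alone: "If AE onset date is on or after treatment start date & within 56 days after treatment stop date". It places no limit at last contact, and it resolves doubt towards On-therapy: "If the study treatment stop date is missing then the AE will be considered to be On-therapy".

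Section 11.6.3, under the time period for On-therapy AEs, starts at treatment start and ends at the earlier of "treatment stop date + 56 days and latest of clinic visits, phone calls and other contact with subject". It then adds that "any events that occurred after the end of this time period are considered to be post the time period for On-therapy AEs". The On-treatment AE period has the same form, ending at the earlier of "treatment stop date, latest of clinic visits, phone calls and other contact with subject".

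Two neighbouring periods in Section 11.6.3 have no such limit for a subject who dies:

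- On-therapy deaths: for subjects known to have died, "use the earliest of the following two dates: treatment stop date + 56 days and date of death".
- Combined On-therapy and Post-therapy AEs: the period extends to the latest of subject contact, "latest non-missing AE start date, latest non-missing AE end date".

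Section 6.2.1 lists contact with someone other than the subject as its own category. Last Study Contact Date in Section 11.6.1 counts such contact. The On-therapy AE period does not mention it.

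**The concern.** Two sections of one plan define the same term, and they can give opposite answers for the same event. Two programmers, each following a different section, would produce different On-therapy tables.

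The disagreement has a direction. When a subject survives an event, the next visit or call normally comes after onset and moves the end of the 11.6.3 period past it. A subject who falls ill and dies between visits may have no later contact. If a relative or a hospital reports the death, that is not contact with the subject. The limit therefore removes events from On-therapy and never adds any, and those most exposed are fatal.

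At stake are the On-therapy SAE displays: fatal SAEs (Table 3.028), treatment-related fatal SAEs (3.032), and the disclosure summaries (3.168 to 3.171 and 3.173). The person-time behind the On-therapy rates is also affected.

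**Working it through.** The SAP states no figure on this point, so there is none to reproduce. The check applies the rules to dates.

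**Rules.** Let S be treatment stop, C the last contact with the subject, A the AE onset and D the date of death.

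- 11.4.2, On-therapy AE: "Study Treatment Start Date ≤ AE Start Date ≤ Study Treatment Stop Date+56 days", so the end is S + 56.
- 11.6.3, On-therapy AE period: end = min(S + 56, C).
- 11.6.3, On-therapy deaths (subject died): end = min(S + 56, D).
- 11.6.3, combined AE period: end = max(C, latest AE start, latest AE end).

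The first two disagree exactly when C < A ≤ S + 56.

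**Illustrative subject** (dates assumed): treatment start 04Jan2016, last contact 05Sep2016, last dose 24Oct2016, fatal SAE onset 27Oct2016, death 30Oct2016. S + 56 = 19Dec2016.

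| Rule | Period ends | Result |
|---|---|---|
| 11.4.2 | 19Dec2016 | SAE is On-therapy |
| 11.6.3 On-therapy AEs | 05Sep2016 | SAE is outside On-therapy |
| 11.6.3 On-therapy deaths | 30Oct2016 | Death is On-therapy |
| 11.6.3 combined AEs | 30Oct2016 | SAE is included |

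Under 11.6.3 the On-therapy AE period closes while the subject is still being dosed.

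**Person-time.** Time is end − start + 1. Under 11.6.3 it is 05Sep2016 − 04Jan2016 + 1 = 246 days. Ending at death gives 30Oct2016 − 04Jan2016 + 1 = 301 days, a difference of 55 days. AE density divides the number of events by total censoring time. If 11.4.2 selected the events while 11.6.3 supplied the censoring date, this SAE would be counted over time that stops 52 days before its onset.

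**Frequency, as an illustration only.** Visits are every 4 months, which at 30.4375 days per month is 121.75 days. Assume that onset is uniform between scheduled contacts, that there is no unscheduled contact with the subject, that death follows onset by L days, and that dosing continues until shortly before onset. The share of such fatal SAEs with no contact between onset and death is 1 − L/121.75:

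| L (days) | 3 | 7 | 14 | 30 | 60 | 90 |
|---|---|---|---|---|---|---|
| Share | 97.5% | 94.3% | 88.5% | 75.4% | 50.7% | 26.1% |

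Unscheduled contact with the subject would lower these shares and missed visits would raise them. The SAP gives neither the lag nor the contact frequency, so this range describes the mechanism and does not estimate the loss.

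**The case against.** The best defence is that the sections have different jobs: 11.4.2 classifies events and 11.6.3 supplies censoring dates. There is support for this. Section 11.4.2 assigns AEs with incomplete dates to a therapy period, Section 11.7.2.2 imputes AE dates to fit the assigned treatment state, and 11.6.3 introduces its periods as the source of the censoring date. Against it, 11.6.3 describes each period as one for capturing AEs and says that later events fall after it. The Table 7 footnotes also define the displays by time period, which is the 11.6.3 term. Even on the favourable reading, the density denominator would stop before the counted event. What stands is that the omission is not certain: it follows if 11.6.3 governs, and the SAP does not say which section does.

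Several stronger inferences are tempting but unsupported:

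- **That On-treatment AEs are caught in the same contradiction.** Section 11.4.2 defines no On-treatment state for AEs. That period has the same limit but feeds only the severe-hypoglycaemia sensitivity analyses (Tables 3.133 and 3.135).
- **That a mismatch between Tables 3.028 and 3.002 proves the fault.** They differ anyway. Table 3.002 uses the ITT population, all causes and date of death. Table 3.028 uses the Safety population and SAEs, from which Section 8.2.1 excludes the main cardiovascular events.
- **That the severe-hypoglycaemia or AESI results would shift materially.** Section 11.6.3 defines severe hypoglycaemia largely by prompt recovery, and survivors normally have a later contact.
- **That a given percentage of fatal SAEs is lost.** The cut-off is any contact with the subject, and the SAP provides for unscheduled visits.
- **That the treatment comparison is biased.** The rule is the same in both arms, and nothing in the SAP shows a differential effect.

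**Conclusion.** The conflict between Sections 11.4.2 and 11.6.3 on On-therapy AEs is established from the text and needs no assumption. If 11.6.3 is followed, a fatal SAE with onset after the last subject contact but no later than stop + 56 days drops out of the On-therapy displays. Compared with 11.4.2, the On-therapy fatal SAE count can only be lower.

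The size cannot be derived from the SAP, and the affected set is limited. The limit binds only when last subject contact precedes stop + 56 days. Myocardial infarction, stroke, heart-failure hospitalization and sudden cardiac death are recorded on event-specific forms and are not SAEs, so the loss concerns other fatal events. A reader might infer that deaths vanish from the report, but they do not: Table 3.027, Listing 17 and the time-to-death analyses (Tables 3.001 to 3.003) are unaffected. The consequence is inconsistent, possibly understated On-therapy safety and disclosure tables. The primary endpoint and all-cause mortality are not touched.

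**What to change.** Amend Section 11.6.3 before unblinding:

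1. State that Section 11.4.2 (onset from treatment start to stop + 56 days) classifies AEs as On-therapy in every display, and remove or reword the sentence that places later events outside the period.
2. For person-time, end the On-therapy AE period at the earlier of stop + 56 days and, for subjects who died, the date of death, or otherwise the last known contact. The end should not precede any counted AE onset. This parallels the On-therapy death period and keeps numerator and denominator on the same time. Extending time only because an event occurred is a fair worry, but for decedents the end is a known date of death, and the onset floor matters only for an event counted after the last known contact.
3. For consistency, apply the same ending rule with the treatment stop date to the On-treatment AE period.

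The cost is a few sentences and one date derivation. No new data are needed.

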11.6.4. Efficacy

Time to Event endpoints

CV Events

- For all CV time to event endpoints (MACE, MACE or Urgent Revascularization for UA, CV Death, MI, Stroke, CV Death or HF Hospitalization), time to event is defined as follows:
For subjects with one or more events, time to event is the date of first event - start date +1.
For subjects with no event, time to event (censored) is the censoring date - start date +1.

Time to Event endpoints
CV Events

Start date and censoring date will be assigned based on the evaluation time period of interest as subsequently specified.
 
The definitions of MACE and other CV events are provided in Section 2 of the protocol. Following are more detailed descriptions of event determination.
 
 Adjudicated MACE events will be determined based on CEC-adjudicated cardiovascular death, myocardial infarction, or stroke. An adjudicated cardiovascular death event will be determined by a corresponding item being recorded in the CEC Death form and will include "Cause of Death" = "Cardiovascular" or "Cause of Death" = "Undetermined Cause of Death"; date of event = date of death. An adjudicated myocardial infarction event will be determined by a corresponding item being recorded in the CEC MI/UA Requiring Hospitalization – Urgent Revascularization form in which "Did MI occur" = "Yes"; date of event = date of MI onset. An adjudicated stroke event will be determined by a corresponding item being recorded on the CEC Stroke/TIA form in which "Did stroke event occur" = "Yes"; date of event = date of stroke onset. 
For time to first occurrence of adjudicated MI, events will include adjudicated MI or death with adjudicated cause = MI. Thus, a fatal event which has adjudicated cause of death = MI but is not adjudicated as MI will be included as an event. A similar approach will be used for time to first occurrence of adjudicated stroke.
 
Investigator-reported MACE events will be determined based on investigator-reported cardiovascular death, myocardial infarction, or stroke. A cardiovascular death event will be determined by a corresponding item being recorded in the Death eCRF form; these will include "Primary Cause of Death" = "Cardiovascular" or "Primary Cause of Death" = "Unknown", and date of event = date of death. A myocardial infarction event will be determined by a corresponding item being recorded in the Cardiac Ischaemic Event eCRF form in which "Final diagnosis" = "MI", and date of event = date of onset of symptoms. A stroke event will be determined by one or more of the following items being recorded in the Stroke / TIA eCRF form: "Type of event" = "Primary ischaemic stroke", "Type of event" = "Primary intracranial hemorrhage", "Type of event" = "Unknown type of stroke", and date of event = start date of neurological symptoms.
 
Because of the way the eCRF is designed, a fatal MI is reported as both an MI and a death. Therefore, the MI event could have an event date that differs from the death date because the subject may have died as a result of the MI but not on the same day. For analysis of first occurrence of MACE, MI, or any other composite endpoint that includes both MI and death, the MI date will be used as the event date. For analysis of CV death only, CV death or hospitalization due to heart failure, and all-cause mortality only, the death date will be used. Similarly, fatal stroke events are reported as both a stroke and a death. For analysis of first occurrence of stroke, or any other composite endpoint that includes stroke and death, the stroke date will be used as the event date. For analysis of CV death only, CV death or hospitalization due to heart failure, and all-cause mortality only, the death date will be used.
 
In the situation that there is a fatal MI (or fatal stroke) that does not have both an adjudicated MI (or stroke) endpoint and a death endpoint with adjudicated cause = MI (or stroke) reported, the


Time to Event endpoints
CV Events

date of the event that is reported and adjudicated as such will be used in the analysis of all relevant endpoints. In addition, situations may occur in which the MI (or stroke) occurs within an analysis period and the death occurs outside of the analysis period; in these situations the endpoint with the date in the analysis period will be used for all relevant endpoints.
 
 • Adjudicated urgent revascularization for unstable angina will be determined by a corresponding item being recorded on the CEC MI/UA Requiring Hospitalization – Urgent Revascularization form in which “Did UA Requiring Hospitalization occur” = “Yes” and “Did the subject have a coronary revascularization during this hospitalization?” = “Yes” and “Classification of Coronary Revascularization”=“Non-Elective” (i.e., Urgent, Emergent or Salvage); date of event = date of coronary revascularization. 
Investigator-reported urgent revascularization for unstable angina will be determined by both of the following types of items being recorded in the eCRF:
 
 ○ “Final diagnosis” = “Unstable Angina” recorded in the Cardiac Ischemic Event eCRF form, ○ “Classification of Urgency” = “Urgent” or “Classification of Urgency” = “Unknown” recorded in the PCI eCRF form or the CABG eCRF form. 
Date of event = PCI date or CABG Procedure date, as applicable. To establish urgency the date of revascularization will be required to be no more than 7 days after the date of the UA.
 
 • Adjudicated HF hospitalization will be determined by a corresponding item being recorded on the CEC HF form in which “Did a hospitalization for heart failure occur?”=“Yes”; date of event = date of hospitalization for heart failure. 
Investigator-reported HF hospitalization will be determined by “Was the subject hospitalized >= 24 hours?”=“Yes” or “Was the subject hospitalized >= 24 hours?”=“Unknown” and “Was the heart failure the primary reason for the hospitalization?” = “Yes” being recorded on the Heart Failure eCRF form.
 
Date of event = date of event/episode recorded on the Heart Failure eCRF form.
 
Because of the way the eCRF is designed, a fatal HF hospitalization is reported as both a HF hospitalization and a death. Therefore, the HF hospitalization event could have an event date that differs from the death date because the subject may have died as a result of the HF but not on the same day.
 
In the situation that there is a fatal HF hospitalization that does not have both an adjudicated HF hospitalization endpoint and a death endpoint with adjudicated cause=HF or Cardiogenic Shock reported, the date of the event that is reported and adjudicated as such will be used in the analysis of CV death or hospitalization due to heart failure.
 
 • For all CV time to event endpoints, if multiple events occur on the same day and it is not clear which event first occurred, then the following order will be applied: 
 MI Urgent revascularization

Time to Event endpoints
CV Events
Hospitalization for heart failure Stroke Death

 First event person-years = (cumulative total time to first event for subjects who have the event + cumulative total of censored time for subjects without the event) / 365.25 First event incidence rate (per 100 person-years) = (100 * number of subjects with at least 1 event) / first event person-years First event absolute rate difference (per 100 person-years) = albiglutide incidence rate (per 100 person-years) – placebo incidence rate (per 100 person-years)
Evaluation Time Periods for CV Endpoints
Time Period for Follow-up of CV Endpoints

 The start date of the time period for capturing CV endpoints is the date of randomization. The end of this time period is the later of the Last CV Assessment Date or the death date in subjects who had not withdrawn consent and had not reached the End of Study. 
Any events that occurred before the start of this time period are considered to be prior to the time period for follow-up of cardiovascular endpoints, and any events that occurred after the end of this time period are considered to be post the time period for follow-up of cardiovascular endpoints.

Time Period for On-treatment CV Endpoints

The start date of the time period for capturing On-treatment CV endpoints is the treatment start date for subjects who received study treatment, and the date of randomization otherwise. The end of this time period is defined as follows:
 
 For subjects who did not receive study treatment, use the date of randomization For subjects who did receive study treatment, use the earliest of the following: 
 treatment stop date Last CV Assessment Date or the death date in subjects who had not withdrawn consent and had not reached the End of Study visit. 
If the censoring date as defined above for On-treatment CV endpoints is after the censoring date as defined for the primary analysis during the time period for follow-up of CV endpoints, then use the censoring date for the primary analysis time period.
 
Any events that occurred before the start of this time period are considered to be prior to the time period for On-treatment CV endpoints, and any events that occurred after the end of this time period are considered to be post the time period for On-treatment CV endpoints.

Time Period for On-therapy CV Endpoints

The start date of the time period for capturing On-therapy CV endpoints is the treatment start date for subjects who received study treatment, and the date of randomization otherwise. The end of this time period is defined as follows:
 
 For subjects who did not receive study treatment, use the date of randomization

Time to Event endpoints
CV Events

For subjects who did receive study treatment, use the earliest of the following:
treatment stop date + 56 daysLast CV Assessment Date or the death date in subjects who had not withdrawn consent and had not reached the End of Study visit.
If the censoring date as defined above for On-therapy CV endpoints is after the censoring date as defined for the primary analysis during the time period for follow-up of CV endpoints, then use the censoring date for the primary analysis time period.
Any events that occurred before the start of this time period are considered to be prior to the time period for On-therapy CV endpoints, and any events that occurred after the end of this time period are considered to be post the time period for On-therapy CV endpoints.
Time Period for Per-Protocol Analysis CV Endpoints
This time period is intended to be used for the Per-Protocol Analysis to include all randomized subjects who provide consent and receive at least one dose of study treatment. The start date of the time period for capturing Per-Protocol Analysis CV endpoints is the treatment start date. The end of this time period is defined as follows: 
Use the earliest of the following:
Earliest of censoring dates as defined in Section 11.1.2Last CV Assessment Date or the death date in subjects who had not withdrawn consent and had not reached the End of Study visit.
If the censoring date as defined above for Per-Protocol Analysis CV endpoints is after the censoring date as defined for the primary analysis during the time period for follow-up of CV endpoints, then use the censoring date for the primary analysis time period.
Any events that occurred before the start of this time period are considered to be prior to the time period for Per-Protocol Analysis CV endpoints, and any events that occurred after the end of this time period are considered to be post the time period for Per-protocol CV endpoints.

Time to Event endpoints
Metabolic Management Events

 Time to insulin and time to prandial insulin are defined as follows: For subjects with an event, time to event is the initiation date – treatment start date + 1. For subjects with no event, time to event (censored) is the censor date – treatment start date +1. 
For subjects not receiving any study treatment, who therefore have no treatment start date, time to event will be determined based on date of randomization.
 
The censor date is the latest of clinic visits and phone calls.
 
The definitions of these events are provided in Section 2 of the protocol. Following are more detailed descriptions of event determination:
 
 An insulin event will require more than 3 months use of insulin for subjects in the NI population and will be determined based on data recorded in the Concomitant Medications eCRF form. Specifically this will require use of any type of insulin for a continuous duration of > 3 months (ie > 3*30.4375 days); this could involve multiple medication entries in the eCRF. In the determination of continuous duration of > 3 months, gaps in useage < 7 days will not be considered a break, but gaps in useage \geq 7 days will be considered a break. A prandial insulin event will require more than 3 months use of prandial insulin (i.e., either a prandial-only insulin or a mixed insulin) for subjects in the BI population and will be determined based on data recorded in the Concomitant Medications eCRF form. Specifically this will require use of prandial or mixed insulin for a continuous duration of > 3 months (ie > 3*30.4375 days); this could involve multiple medication entries in the eCRF. In the determination of continuous duration of > 3 months, gaps in useage < 7 days will not be considered a break, but gaps in useage \geq 7 days will be considered a break. Insulin categories are shown in Section 11.13. Initiation date is the date of the earliest medication use after treatment start date. Duration of use = latest stop date of medication – initiation date +1. If a medication stop date is missing, then the date of study completion will be used. 
 Time to first occurrence of a clinically important microvascular event is defined as follows: For subjects with an event, time to event is the first event date – date of randomization +1. For subjects with no event, time to event (censored) is the censor date – date of randomization +1. 
The censor date is the latest of clinic visits and phone calls.
 
The first event date is the date of first occurrence of a clinically important microvascular event. The definition of clinically important microvascular events is provided in Section 6.2.4 of the protocol. Based on this definition, such an event will be determined by one or more of the following items being recorded in the eCRF with a date on or after date of randomization:
 
 Need for renal transplant or dialysis (Renal Impairment eCRF form, Event Treatment/Management: “Treatment required for the renal impairment” = “Renal transplantation”, “Haemodialysis”, or “Peritoneal dialysis”); event date is the corresponding treatment start date. Temporary renal replacement therapy will not

Time to Event endpoints	
Metabolic Management Events	
	
qualify as an event; such cases will be identified by recording as "Renal Replacement" and also "Other, Specify" with corresponding text description.
 
 ○ New diabetes-related blindness (Diabetic Eye Disease Event eCRF form, Visual Function, "Severity of Visual Impairment"= "Able to count fingers or worse (Blindness)" and also "Does the subject have visual impairment (after best possible correction with glasses)"="Yes" and also "Is the visual impairment diabetes related"="Yes"); event date is the date of diagnosis of new or worsening diabetic retinopathy/maculopathy. ○ Procedures (Diabetic Eye Disease Event eCRF form, Treatment: "Anti-VEGF Treatment"="Yes", "Photocoagulation"="Yes", or "Vitrectomy" indicated in one or both eyes); event date is the corresponding date of treatment.

Composite Metabolic Endpoint	
	
 • The composite metabolic endpoint is defined in Section 2 of the protocol. Subjects will be defined as achieving the composite metabolic endpoint based on the following criteria: glycaemic control ($\text{HbA1c} \leq 7.0\%$ at final assessment) with no severe hypoglycaemic incidents and weight gain <5% from baseline • The final assessment is defined as the latest post-baseline assessment of both HbA1c and weight (on same date) in the corresponding time period (either overall or On-treatment). • Severe hypoglycaemic incidents will be determined by an event being recorded in the Severe Hypoglycaemic Event eCRF form with a start date that is post-baseline and is on or before the final assessment date defined above for the corresponding time period (either overall or On-treatment).

HbA1c	
	
 • For HbA1c measured in mmol/mol, values will be converted to % based on the following [Geistanger, 2008]: $\text{HbA1c (\%)} = [0.09148 * \text{HbA1c (mmol/mol)}] + 2.152$ 
In a similar manner, for HbA1c measured in %, values will be converted to mmol/mol based on solving the above equation accordingly:
 $\text{HbA1c (mmol/mol)} = [\text{HbA1c (\%)} - 2.152] / 0.09148$

Time to Event endpoints	
TIA	
	
 • Time to first TIA and time to first Stroke or TIA are defined as follows: For subjects with an event, time to event is the date of first event – date of randomization +1. For subjects with no event, time to event (censored) is the Last CV Assessment Date – date of randomization +1.

Time to Event endpoints	
TIA	

 Definitions of adjudicated stroke and investigator-reported stroke have been previously provided. An adjudicated TIA event will be determined by a corresponding item being recorded on the CEC Stroke/TIA form in which “Did a TIA event occur” = “Yes”; date of event = date of TIA onset. An investigator-reported TIA event will be determined by the following item being recorded in the Stroke / TIA eCRF form: “Type of event”=“Transient ischaemic attack (TIA)”; date of event = start date of neurological symptoms. 	

 First event person-years = (cumulative total time to first event for subjects who have the event + cumulative total of censored time for subjects without the event) / 365.25 First event incidence rate (per 100 person-years) = (100 * number of subjects with at least 1 event) / first event person-years First event absolute rate difference (per 100 person-years) = albiglutide incidence rate (per 100 person-years) – placebo incidence rate (per 100 person-years) 	
Evaluation Time Period for TIA Endpoints	

 The evaluation time period for capturing TIA endpoints is the CV Follow-up time period (previously defined). 
Any events that occurred before the start of this time period are considered to be prior to the time period for follow-up of TIA endpoints, and any events that occurred after the end of this time period are considered to be post the time period for follow-up of TIA endpoints.
	

